6.1.2 Full / Safety Population

The Full and Safety Populations consist of all enrolled subjects who received at least one dose of deflazacort.

6.1.3 Pharmacokinetic Population

The pharmacokinetic (PK) population includes all enrolled subjects who received at least 1 dose of deflazacort and had at least one PK profile.

6.2 Derived Data

This section describes the derivations required for statistical analysis. Unless otherwise stated, variables derived in the source data will not be re-calculated.

6.2.1 Age

QMD Ref: Worldwide-TMP-ST-005-7.0 Effective: 12Aug2019	Governing QMD: Worldwide-SOP-ST-001
Confidentiality Statement	
This document is the property of Worldwide Clinical Trials Inc. and may not be duplicated, copied, altered or removed from company without prior approval from Worldwide Quality Assurance or in compliance with Worldwide Standard Operating Procedures.	

Worldwide Clinical Trials Controlled Quality Management Document		
 WORLDWIDE CLINICAL TRIALS	Sponsor:	PTC Therapeutics, Inc
	Protocol Number:	PTCEMF-GD-004
STATISTICAL ANALYSIS PLAN		

Age at time of informed consent as collected on the CRF will be used to represent age of subject in the study.

6.2.2 Race

Where more than one race category has been selected for a subject, these race categories will be combined into a single category labeled “Multiple Race” in the summary tables. The listings will reflect the original selected categories.

6.2.3 Baseline

Baseline is defined as the last non-missing observation (either scheduled, unscheduled, or repeated) prior to the first dose of deflazacort.

The time to climb 4 stairs: it is performed twice at each visit. The maximum value prior to the first dose of deflazacort will be considered as baseline.

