## **9 STATISTICAL CONSIDERATIONS**

### **9.1 Statistical Hypothesis**

No hypothesis will be tested in this study.

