6.2.7 Change from Baseline

Change from baseline for any variable at a given visit will be calculated by subtracting the baseline value (last non-missing scheduled, unscheduled or repeat value before the first dose of deflazacort) of the variable from the value of the variable at the given visit. If there is no baseline or screening value, then the change from baseline will be missing.

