6.10.1 Analysis of Primary Endpoint

The actual value and the change from baseline in 4-stair climb time, measured in seconds will be summarized descriptively (number of non-missing observations (n), mean, standard deviation, minimum, median, and maximum) at each assessment visit for the Full Population. The time to climb 4 stairs is performed twice at each visit. The maximum value at each visit will be used for summary and analysis purposes.

In addition, the 95% confidence interval for the mean change from baseline after 26 weeks of deflazacort treatment will be provided.

A waterfall plot of the change in 4- stair climb time at Week 26 will be provided.

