6.10.2 Analysis of Secondary Endpoints

The following secondary endpoints will be summarized similar to the primary endpoint by study visits for the actual value and the change from baseline.

- Forced vital capacity (FVC)
- 2-minute walk test
- Time to up and go
- Time to descent 4 stairs
- Time to run/walk 10 meters
- Maximal inspiratory pressure (MIP)
- Maximal expiratory pressure (MEP)
- Hand-held myometry

For all endpoints with repeated measurements, the maximum value at each visit will be used for summary and analysis purposes.

Similar as the primary endpoint, summary statistics such as n, mean, standard deviation, median, minimum and maximum, and the 95% confidence interval for the mean change at Week 26 will be provided for all secondary endpoints.

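### For any secondary endpoint with repeated measurements at a visit, the SAP read literally subtracts the last pre-dose value from a later visit's maximum, so the two sides of the change score differ

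*SAP*

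**What the plan says.** Three parts of the SAP bear on the change score of a secondary endpoint.

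- **Baseline (6.2.3).** "Baseline is defined as the last non-missing observation (either scheduled, unscheduled, or repeated) prior to the first dose of deflazacort". One exception follows, for the 4-stair climb, which is done twice per visit: "The maximum value prior to the first dose of deflazacort will be considered as baseline". No secondary endpoint has an exception.
- **Change (6.2.7).** For every variable, the quantity subtracted is the "last non-missing scheduled, unscheduled or repeat value before the first dose of deflazacort".
- **Visit value (6.10.2).** "For all endpoints with repeated measurements, the maximum value at each visit will be used for summary and analysis purposes". The same section adds that "the 95% confidence interval for the mean change at Week 26 will be provided for all secondary endpoints".

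SAP Section 9, which lists departures from the protocol analysis, does not reconcile these rules. The only test that either document describes as done more than once per visit is the 4-stair climb. Conduct of the pulmonary and timed function tests is left to separate manuals.

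**The concern.** If a secondary endpoint has several recorded attempts per visit and the rules are programmed as written, the two halves of the change score are different statistics: a maximum after dosing and a single attempt before it. A maximum exceeds a single attempt on average, so the mean change moves upward with no drug effect.

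Where higher is better (FVC, MIP, MEP, myometry, 2-minute walk distance) this looks like benefit. For a repeated timed test it looks like slowing. Pulmonary function is the first secondary objective. The summaries are single-arm, and SAP Section 6 confines placebo-period data to listings, so no comparison group absorbs the shift.

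The point concerns only the secondary endpoints. The primary endpoint has its own baseline rule, and whether a maximum or a mean is the better summary is a different question.

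**Working it through.** **The plan's own figure.** The only computed precision in the plan is for the primary endpoint: 1.96 × 0.7 / √30 = 0.2505, which reproduces the stated −0.25 to 0.25 seconds. It is not affected by this point. The plan gives no corresponding figure for a secondary endpoint.

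**Inputs**
- Baseline and change rules: SAP 6.2.3 and 6.2.7. Visit rule: SAP 6.10.2.
- Subjects: 11 enrolled (SAP Sections 1 and 9).
- Recorded attempts per visit, k: not in the documents. Assumed range 1 to 3.
- Within-visit SD, s: not in the documents. Results are therefore in units of s and cannot be turned into litres, cmH2O or seconds.

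**Step 1: direction.** Read literally, change = max(k attempts at the visit) − (last attempt before dosing). If nothing changes between visits, its expectation is E[max] − E[last]. A session's maximum is never below its last attempt, so the expectation cannot be negative. It is positive unless the last attempt is always the best. No normality is needed for this.

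**Step 2: size.** With independent normal attempts and no trend within a session:
- k = 1: 0
- k = 2: s/√π = 0.564 s
- k = 3: 3s/(2√π) = 0.846 s

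The no-trend assumption matters. In simulation with k = 3, if attempts improve by 0.5 s or 1 s per attempt, the bias falls to about 0.45 s or 0.22 s. Fatigue within the session raises it.

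**Step 3: effect on the interval.** This is a simulation with n = 11, no true change and t-based 95% intervals. Visit-to-visit variation of SD 0.5 s, 1 s or 2 s was added in two ways: (A) once, to the change; (B) separately at each of the two visits. The table gives the share of trials whose interval lies wholly above zero (nominal 2.5%).

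| Attempts | Model | 0.5 s | 1 s | 2 s |
|---|---|---|---|---|
| 2 | A | 23% | 18% | 11% |
| 2 | B | 21% | 14% | 8% |
| 3 | A | 47% | 35% | 19% |
| 3 | B | 42% | 27% | 13% |

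With k = 1 the share stays at the nominal 2.5%.

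**Step 4: same rule on both sides.** Taking the maximum at baseline as well brings the mean change back to zero. The interval then excludes zero, in either direction, in 4.7% to 5.1% of trials.

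**The case against.** **The visit rule may already cover baseline.** The schedule labels Visit 1 as baseline. SAP 6.2.6 makes the start of open label analysis Visit 1 for former placebo subjects, and 6.10.2 summarises actual values by visit. One can read the sections together as: collapse each visit to its maximum, then take the last pre-dose value. That reading is possible and may be what was meant. It does not clear the text, because 6.2.7 still names the last repeat value as the one subtracted. SAP 6.10.1 also uses the same wording for the stair climb, "The maximum value at each visit will be used for summary and analysis purposes", and that test was nevertheless given a separate baseline rule. This second argument is the weaker one, since the stair climb may have been singled out only because it is the one test known to be done twice. And if Visit 1 is displayed as a maximum while 6.2.7 governs the subtraction, the mean change will not equal the difference of the displayed means, even in the same subjects.

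**A repeat may mean a re-done assessment, not an attempt within a test.** This is also possible. The SAP does not define the term.

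**There may be no repeats in the data.** SAP 6.2 leaves variables already derived in the source data as they are. If the source holds one best effort per visit, the bias is zero. This stands, and it limits the point. On the other side, 6.10.2 writes a rule for repeated measurements in the secondary-endpoint section, so the SAP expects that some may exist.

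**Little depends on the interval.** Protocol 9.1 says "No hypothesis will be tested in this study", the study stopped with 11 subjects for reasons unrelated to efficacy or safety, and all efficacy data are listed by subject. This limits the consequences. It does not remove the problem, because the shift is in the estimate itself.

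**Conclusion.** The point holds in conditional form. For a secondary endpoint with more than one recorded value per visit, the literal SAP rules give a change score that compares a maximum with a single value. The resulting shift goes one way. Its size is zero for one value per visit, about +0.56 within-visit SD for two attempts and about +0.85 for three, the last two resting on independent normal attempts with no within-session trend.

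The interval rates of 8% to 23% (two attempts) and 13% to 47% (three) illustrate what could happen with 11 subjects. They depend on the assumed attempts, error model and visit-to-visit SDs of 0.5 to 2 within-visit SDs, and they are not estimates for this trial.

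A reader might infer that FVC, MIP, MEP and myometry will show false gains. The documents do not support that: they never say that these tests have more than one recorded attempt per visit, and they give no within-visit SD. What they do establish is a mismatch between rules that should be corrected, together with the direction in which it would act.

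**What to change.** In SAP 6.2.3 and 6.2.7, state that for every secondary endpoint with repeated measurements one value per visit is derived first, by the same rule at every visit including baseline, and that baseline is that derived value at the last visit before the first deflazacort dose. Whatever summary 6.10.2 uses then applies to both sides of the change. Confirm from the test manuals and the database which endpoints hold more than one value per visit, and check the baseline programs against the revised rule.

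The cost is one sentence in the SAP and a programming check, with no new data. The downside is that reported pulmonary and strength changes may become less favourable.

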**Abbreviations:** AE, adverse event; BP, blood pressure; BMI, body mass index; DEXA; dual-energy X-ray absorptiometry; ECG, electrocardiogram; ET, early termination; FKRP, fukutin-related protein gene; FVC, forced vital capacity; HCG; human chorionic gonadotropin; HR, heart rate; INQoL, Individualized Neuromuscular Quality of Life; IRT, Interactive Response Technology; MEP, maximal expiratory pressure; MIP, maximal inspiratory pressure; MRI, magnetic resonance imaging; PD, pharmacodynamic; PK, pharmacokinetic; SAE, serious adverse event

**Note:** See also Section 3.4 for explanation of the transition from Protocol Version 3.0 to Version 4.0.

 Screening procedures must take place within 42 days of baseline visit (Visit 1). No study-related procedures should be performed prior to the signature of the informed consent document(s).

 Any screening procedure completed within and including 7 days of Visit 1, with the exception of the time to climb 4 stairs, can serve as baseline and does not need to be repeated at Visit 1. The time to climb 4 stairs must always be performed twice at the baseline visit and all other visits. The second 4 stair climb

- test should be done a minimum of 5 minutes after the prior test, or any other physical activity. The baseline visit may be split into two consecutive days.
-  At Visit 3, subjects initially randomized to deflazacort will continue deflazacort treatment while subjects originally randomized to placebo will initiate deflazacort treatment at a target dose of 0.6 mg/kg/day. For placebo subjects, all assessments will be performed prior to first dose of deflazacort (See also Section 3.4 for explanation of the transition from Protocol Version 3.0 to Version 4.0).

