Pulmonary Function Testing ¹²		X			X		X	X		Pulmonary function will be evaluated by spirometry. Pulmonary function test procedures will be detailed in a manual separate from this protocol. The following pulmonary function tests will be evaluated: FVC, MIP, and MEP.
Biomarker testing (Bone Health Assays) ¹³		X		X	X			X		
INQoL Questionnaire ¹⁴		X			X			X		
MRI ^{12,15}		X		X	X			X		Dixon MRI and T2 MRI will evaluate muscular fat fraction and inflammation, respectively, of selected lower limb muscles. Details will be further elucidated in an MRI manual separate from this protocol.
Study Drug Administration										
Dispense Drug via IRT		X		X	X		X			
Unused Drug Return/ Compliance				X	X		X	X	X ⁵	

Abbreviations: AE, adverse event; BP, blood pressure; BMI, body mass index; DEXA, dual-energy X-ray absorptiometry; ECG, electrocardiogram; ET, early termination; FKR, fukutin-related protein gene; FVC, forced vital capacity; HCG, human chorionic gonadotropin; HR, heart rate; INQoL, Individualized Neuromuscular Quality of Life; IRT, Interactive Response Technology; MEP, maximal expiratory pressure; MIP, maximal inspiratory pressure; MRI, magnetic resonance imaging; PD, pharmacodynamic; PK, pharmacokinetic; SAE, serious adverse event

Note: See also Section 3.4 for explanation of the transition from Protocol Version 3.0 to Version 4.0.

- ¹ Screening procedures must take place within 42 days of baseline visit (Visit 1). No study-related procedures should be performed prior to the signature of the informed consent document(s).
- ² Any screening procedure completed within and including 7 days of Visit 1, with the exception of the time to climb 4 stairs, can serve as baseline and does not need to be repeated at Visit 1. The time to climb 4 stairs must always be performed twice at the baseline visit and all other visits. The second 4 stair climb test should be done a minimum of 5 minutes after the prior test, or any other physical activity. The baseline visit may be split into two consecutive days.
- ³ At Visit 3, subjects initially randomized to deflazacort will continue deflazacort treatment while subjects originally randomized to placebo will initiate deflazacort treatment at a target dose of 0.6 mg/kg/day. For placebo subjects, all assessments will be performed prior to first dose of deflazacort (See also Section 3.4 for explanation of the transition from Protocol Version 3.0 to Version 4.0).

QMD Ref: Worldwide-TMP-ST-005-7.0 Effective: 12Aug2019

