- ⁷ Chemistry assessments include sodium, potassium, chloride, bicarbonate, blood urea nitrogen (urea), creatinine, uric acid, protein (total), albumin, bilirubin (total), aspartate transaminase, alanine transaminase, gamma glutamyl transpeptidase, alkaline phosphatase, lactate dehydrogenase, glucose (fasting), hemoglobin A1c, calcium, phosphate, magnesium, creatine kinase, cholesterol, high density lipoproteins, low density lipoproteins (calculated), and triglycerides.
- ⁸ Only for women of child-bearing potential.
- ⁹ Ophthalmological examination includes a glaucoma assessment, cataract assessment, and intraocular pressure measurement.
- ¹⁰ If possible, both X-ray and DEXA should be performed; however, only an X-ray or DEXA is acceptable if the other technology is not available or prohibited per local ethical/regulatory decree.
- ¹¹ The pre-dose blood draw will be taken within 2 hours before dosing. For timepoints up to 2-hours post dose, a window of ± 10 minute will be allowed for blood collection. From 4 hours to 6 hours post samples, a window of ± 30 minutes will be allowed.
- ¹² Efficacy and PD assessments will be performed post-daily-dose at each clinic visit, except for the baseline visit (Visit 1). At screening and baseline visits, the ability to ascend 4 stairs must be ≥ 2.5 and ≤ 8 seconds. In addition, the 4-stair climb will be performed twice at each visit. The second test should be done a minimum of 5 minutes after the prior test (or any other physical activity). The two 4-stair climb results must be within 20% of one another. If they are not the Medical Monitor should be contacted.
- ¹³ Biomarker testing (bone health assays) include bone alkaline phosphatase (BAP), Beta-CrossLaps (Beta-CTx), insulin-like growth factor-1 (IGF1), parathyroid hormone (PTH) intact, aldosterone, and vitamin D (Serum 25-hydroxyvitamin D3).
- ¹⁴ INQoL will be performed before the first dose at baseline and after 26 weeks of treatment, when possible.
- ¹⁵ Dixon MRI and T2 MRI will be conducted at a subset of sites that have been pre-qualified by a central imaging vendor to perform this assessment. To be pre-qualified, a site must have access to whole-body scanner and appropriate personnel and must have been trained on the procedure for data acquisition. MRI data will be analyzed centrally.

QMD Ref: Worldwide-TMP-ST-005-7.0 Effective: 12Aug2019	Governing QMD: Worldwide-SOP-ST-001
Confidentiality Statement	

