6 STATISTICAL ANALYSES

Subjects will be pooled in all efficacy and safety analyses regardless of the protocol version they enrolled. No summary tables will be provided for the events or assessments occurred during the placebo period for subjects who enrolled prior to protocol version 4.0 and randomized to placebo group. All events or assessments occurred during the placebo period will be presented in the by-subject listings only.

Subjects who took at least one dose of deflazacort will be pooled in the safety and efficacy summaries. Safety and efficacy listings will be provided including the events and measurements occurred during placebo period.

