6.2.6 Study Visits

Nominal visits will be used as the analysis visits for subjects who were randomized to deflazacort under protocol version 3.0 or enrolled under protocol version 4.0.

For subjects who were randomized to placebo under protocol version 3.0 and then reconsented to receive deflazacort under protocol version 4.0, the nominal visits will be remapped to have the start of the open label visit as the first analysis visit. For example:

Nominal visit for placebo subjects	Analysis visit
V1	
V2	
V3 (Start of open label)	V1
V4	V2

QMD Ref: Worldwide-TMP-ST-005-7.0 Effective: 12Aug2019	Governing QMD: Worldwide-SOP-ST-001
Confidentiality Statement	
This document is the property of Worldwide Clinical Trials Inc. and may not be duplicated, copied, altered or removed from company without prior approval from Worldwide Quality Assurance or in compliance with Worldwide Standard Operating Procedures.	

Worldwide Clinical Trials Controlled Quality Management Document		
 WORLDWIDE CLINICAL TRIALS	Sponsor:	PTC Therapeutics, Inc
	Protocol Number:	PTCEMF-GD-004
STATISTICAL ANALYSIS PLAN		

V5	V3
...	...

All summaries will be based on analysis visits. Assessment taken under unscheduled visits or nominal visits during the placebo period for subjects who randomized to placebo group will be presented in the subject listings only.

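### SAP 6.2.3 does not tie the 4-stair baseline to one visit: as written it sets the slowest of at least four pre-dose climbs against the slower of two at follow-up, which tilts the primary change toward improvement

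*SAP*

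**What the plan says.** The primary analysis is the mean change from baseline in 4-stair climb time at Week 26 with its 95% CI (SAP 6.10.1). Four places bear on the baseline.

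- **SAP 6.2.3** first gives a general rule, the last non-missing observation before deflazacort. It then gives the 4-stair climb its own rule: "The maximum value prior to the first dose of deflazacort will be considered as baseline". No visit is named.
- **SAP 6.10.1** limits the follow-up value to one visit: "The maximum value at each visit will be used for summary and analysis purposes".
- **SAP Figure 1 and the protocol's Schedule of Events** place timed function tests at both Screening and Visit 1. Footnote 12 says "In addition, the 4-stair climb will be performed twice at each visit", and footnote 2 says "The time to climb 4 stairs must always be performed twice at the baseline visit and all other visits". Footnote 2 also separates the climb from the other Screening procedures, which, "with the exception of the time to climb 4 stairs, can serve as baseline and does not need to be repeated at Visit 1". Protocol 3.1 repeats that exception.
- **SAP 6.2.7** calculates change for any variable from the "last non-missing scheduled, unscheduled or repeat value before the first dose of deflazacort", with no exception for the 4-stair climb.

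For subjects first randomized to placebo, SAP 6 says "No summary tables will be provided for the events or assessments occurred during the placebo period", and under SAP 6.2.6 "the nominal visits will be remapped to have the start of the open label visit as the first analysis visit". SAP 6.3 likewise keeps the placebo period in listings. SAP 9 does not list the 4-stair baseline rule as a departure from the protocol.

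**The concern.** The outcome is a time, so the maximum is the slowest climb and a negative change is improvement. The more climbs that enter a maximum, the larger it tends to be. If baseline draws on two visits and follow-up on one, an apparent improvement arises from the derivation alone. It would go straight into the primary estimate, and without a comparator nothing in the results would separate it from a drug effect.

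The rule as written also readmits Screening climbs, which footnote 2 keeps out of the baseline. In addition, former placebo subjects, whose earlier visits SAP 6, 6.2.6 and 6.3 set aside, would have a two-climb baseline pooled with four-climb baselines from the others.

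**Working it through.** **The plan's own figure.** SAP 4 assumes mean change 0, SD 0.7 s and N = 30. Half-width = 1.96 × 0.7/√30 = 0.2505 s, which reproduces the stated ±0.25 s (the t-based value is 0.261 s). For the 11 subjects enrolled (SAP 1), if all have Week 26 data: t(0.975, 10) × 0.7/√11 = 0.470 s.

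**Direction.** Let S1, S2 be the Screening climbs, V1, V2 the Visit 1 climbs, and F the follow-up maximum. Then max(S1, S2, V1, V2) ≥ max(V1, V2) for every subject. So F minus the literal baseline is never above F minus the Visit 1 baseline. No noise model is needed.

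**Size in SD units, no true change.** Let σ be the total within-subject SD of a climb, taken as normal. The expected maximum of k independent climbs is 0.564σ for k = 2 and 1.029σ for k = 4.

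- Independent climbs: shift = 0.564σ − 1.029σ = −0.465σ.
- Half of the within-subject variance is visit-to-visit (simulated): −0.517σ.
- Limit, all of it visit-to-visit: −0.564σ.
- Both sides limited to one visit: 0.

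If nothing changes between Screening and Visit 1, the two visits are exchangeable. A Screening climb then sets the literal baseline in about half of the Visit 1 starters.

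**Size in seconds, σ assumed.** The documents do not give σ. For 0.1 to 0.5 s the shift is −0.05 to −0.23 s (independent climbs) or −0.06 to −0.28 s (limit).

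**Size tied to the SAP's SD of change.** Take 0.7 s as the SD of the change in per-visit maxima, and let f be the share of that variance that is within-subject noise. With independent climbs, the noise SD of the single-visit change is √[2(1 − 1/π)]σ = 1.168σ, and 0.465/1.168 × 0.7 = 0.279. In the limit it is √2σ, and 0.564/1.414 × 0.7 = 0.279. Simulated shares in between give 0.278 to 0.279. So the shift is about −0.279√f s, whatever the within-visit correlation.

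| f (assumed) | Shift per Visit 1 starter | Share of 0.470 s | Pooled, if 6 of 11 started at Visit 1 |
|---|---|---|---|
| 0.1 | −0.09 s | 19% | −0.05 s |
| 0.25 | −0.14 s | 30% | −0.08 s |
| 0.5 | −0.20 s | 42% | −0.11 s |

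The upper bound, f = 1, is −0.28 s. The share of Visit 1 starters is not in the documents, so 6 of 11 is only an illustration. The pooled column gives former placebo subjects a two-climb baseline and hence no shift.

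**If SAP 6.2.7 were followed instead.** Baseline would be the last single climb, and the shift is +0.564 × the within-visit replicate SD, toward worsening. For an assumed 0.1 to 0.3 s this is +0.06 to +0.17 s. The 20% agreement rule in footnote 12 gives a rough check on that range. If 95% of pairs agree within 20%, the replicate SD is at most 0.2m/(1.96√2) for a climb of m seconds: 0.18 s at 2.5 s, 0.29 s at 4 s and 0.58 s at 8 s. The last of these would give +0.33 s.

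**The case against.** The best counter-argument is that the single-visit reading is the natural one. The sentence just before the rule says the climb is done twice at each visit, so the maximum may be meant only to choose between two replicates. SAP 6.10.1 and footnote 2 point the same way, and under that reading the bias is zero. This shows what was probably intended, and nothing here shows how the analysis was programmed. It does not settle the text. The authors limited the maximum to a visit in 6.10.1 and did not in 6.2.3, and 6.2.7 supplies a third rule whose shift has the opposite sign. The specific rule in 6.2.3 would normally override 6.2.7, but no cross-reference says so.

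It can also be said that context is used to limit former placebo subjects to two climbs but not to limit Visit 1 starters. The difference is that SAP 6, 6.2.6 and 6.3 expressly send placebo-period assessments to listings, and no analysis rule does the same for Screening. If those sections did not govern the baseline, these subjects would have 6 to 8 pre-dose climbs and a larger shift, −0.70σ to −0.86σ with independent climbs.

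Two limits do stand. Every figure in seconds rests on an assumed σ or f, and fewer than 11 subjects at Week 26 would widen the interval and lower the percentages. The consequence is also bounded: no hypothesis is tested, and the per-visit values and listings allow either baseline to be re-derived.

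**Conclusion.** The concern holds. As written, SAP 6.2.3 compares the slowest of at least four climbs with the slower of two for anyone who starts at Visit 1. It conflicts with footnote 2 and can only move the primary change toward improvement. The direction is certain under that wording. The size is not fixed by the documents: −0.47σ to −0.56σ per Visit 1 starter, or about −0.09 to −0.20 s for f between 0.1 and 0.5, diluted by the share of subjects who did not start at Visit 1. That is a material part of a 0.47 s half-width, though smaller than it. The fault is correctable and lies in a planned primary derivation. It should be fixed before the result is reported.

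**What to change.** - **SAP 6.2.3:** define the 4-stair baseline as the maximum of the two climbs at the last visit before the first deflazacort dose. That is Visit 1, or the pre-dose assessment at nominal Visit 3 for former placebo subjects. State that Screening and earlier placebo-period climbs do not enter it.
- **SAP 6.2.7:** refer to 6.2.3 instead of restating the last-value rule.
- **SAP 6.10:** reword the sentence that sends former placebo subjects' data from before deflazacort to listings only. Read literally, it also removes the pre-dose Visit 3 assessment that is their baseline.
- **SAP 6.10.2:** for secondary endpoints with replicates, state that baseline uses the same per-visit maximum as the on-treatment visits.

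The cost is a few sentences and no new data. The planned precision of ±0.25 s is unaffected. The change removes only the derivation artefact; practice and open-label effects remain.
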